5.4 Patient Withdrawal

In accordance with the Declaration of Helsinki, the investigator must explain to the patient that they have the right to withdraw from the study at any time, and that this will in no way prejudice their future treatment. The reason for any kind of withdrawal must be recorded on the appropriate CRF.

There will be two main categories for withdrawals from the study:

Complete withdrawal (i.e. stopping investigational product and also continued efficacy and safety evaluations)

Standard reasons for withdrawing from further participation in the study and from the follow-up visits (and <e.g. blood tests>) may be:

- Patient's decision (withdrawal of consent to participate)
- Patient lost to follow-up

Withdrawals from investigational product (i.e. stopping one or several investigational products, but continuing follow-up visits, including efficacy and safety evaluations)

Standard reasons from withdrawing from taking further investigational product, but continuing follow-up visits and safety evaluations may be:

- Unacceptable adverse events
- Patient request
- Investigator's discretion
- Patient lost to follow-up/non-attendance
- Intercurrent illness
- The patient becomes pregnant

Thus subcutaneous GAD-Alum should not be given to the patient if the patient after inclusion in the study develops/experiences

- Brain damage, epilepsia, head trauma, neurological disease
- Any active, serious hormonal disease other than T1D
- Other severe autoimmune disease (except celiac disease which is accepted for inclusion.)
- Immune-suppressive treatment
- Cancer, cancer treatment
- Any other diabetes drugs other than insulin
- Any vaccination
- Drug/alcohol abuse
- Become pregnant or is no longer willing to use safe contraceptives during the study

Etanercept should not be continued if the patient after inclusion in the study develops/experiences

- Allergic reactions to etanercept or any of the excipients
- Other severe reactions to etanercept injections
- Sustained elevations of creatinine of liver function tests,
- Evidence of cardiac disorder
- Severe infections, such as sepsis, meningitis or osteomyelitis

- Suspected, latent or manifest tuberculosis
- Suspected or manifest viral hepatitis
- Severe lymphopenia
- Anemia
- Thrombocytopenia
- Malignancy
- Urticaria
- Varicella Zoster virus exposure or infection
- Live vaccines such as morbilli, parotitis, rubella, live polio, BCG and others

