6.2 Assessments and Procedures

- 1. Standard insulin treatment, education and psychosocial support for newly diagnosed T1D patients.
- 2. Normalization of fluid, electrolyte and acid-base balance.
- 3. Thereafter information about the study.
- 4. When the patients and parent(s) / legal guardian(s) have given their informed consent, at the latest 100 days after diagnosis, screening is performed with a fasting venous sample from patients who are eligible according to other criteria than C-peptide and GADA concentrations (Visit 1). Patients are also tested for tuberculosis, renal or liver disease at this visit (see section 5.3.1 and 5.3.2 above).
- 5. At Visit 2 (Baseline), Visit 6 (6 months), Visit 8 (15 months) and Visit 9 (30 months), assessment of residual endogenous insulin secretion by MMTT.
- 6. Blood sampling for Vitamin D in serum at Visit 1, and then after one month of treatment at Visit 3 (before the first GAD-alum treatment) and at Visit 8 (15 months)
- 7. HbA1c, safety (haematology and chemistry), autoantibody titres (GAD65, IA-2), immunology are followed by blood samples at every visit.
- 8. Exogenous insulin dose/24 hours, AEs and concomitant medication are registered at every visit.
- 9. Self-reported hypoglycaemia (defined as needing help from others and/or seizures and/or unconscious) registered at every Study Visit.
- 10. Any symptoms or signs of other medical problems should be treated at the discretion of the clinical doctor. Thus if a patient experiences symptoms and/or signs of infection that should be treated lege artis.

Examinations will be performed according to table 2 in Section 7 below, and in the order outlined in the case report form (CRF).

6.2.1 All Visits, Visit 1 through 9

Note that the patient should attend all study visits in the morning following an overnight fast (> 10 hours, water allowed).

For patients with evidence of an infection (including fever), the complete visit should be postponed for 5 days or until the patient has recovered.

6.2.2 Injections with GAD-Alum (Diamyd), Visits 3 and 4

Injections of GAD-alum (Diamyd) will be administered at Visits 3 and 4, subcutaneously in the stomach area.

After the injection, the patient shall remain in the vicinity of the study site for the next hour, and the injection site will be examined by investigator/study nurse 1 hour post injection.

6.2.3 Mixed Meal Tolerance Test (MMTT), Visits 2, 6, 8 and 9

The MMTT must be performed according to the instructions in the CRF.

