6.7 Safety Plan

To ensure subject safety a Safety Plan is in place describing the study specific safety measures that are to be taken during the study. This Safety Plan must be used in conjunction with this protocol.

The purpose of the Safety Plan is to ensure:

- the safety of patients receiving etanercept, Diamyd and vitamin D treatment in the study.
- that appropriately qualified medical personnel are readily available to advise on trial related medical questions or problems regarding the study drug treatment in the above mentioned study.
- that study personnel are educated about know side effects of the study drug treatment and how to handle them.
- that patients and their parents/legal guardian(s) are given information about possible side effects.

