7.1 Visits

The first visit, the screening visit (Visit 1) should be performed 10 to 21 days before planned Visit 2 (Baseline). Visit 3 and 4 should then be scheduled with a visit window of \pm 3days (first and second injection with GAD-Alum) and of \pm 7 days for Visit 5 and 6. For Visit 7, 8 and 9 the visit window is extended to \pm 14 days.

Please note that all visits, except Visit 4 must be calculated from the baseline visit (Visit 2) according to the visit schedule. For Visit 4 (second GAD-Alum administration) the visit date must be set in accordance with Visit 3 (i.e. the first GAD-Alum administration) so that the first and second GAD-Alum doses will be 30 days apart (\pm 3 days). Please also note that the visits must be performed within the visit windows to comply with the study protocol.

8 Study Medication

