9.1 Assessments

9.1.1 Variables

The tolerability and safety assessments includes occurrence of adverse events (AEs), laboratory measurements, physical examinations and neurological assessments (See section 6.3-6.7)

Adverse events will be recorded by the physician at every visit throughout the study.

Blood tests for safety:

- Chemistry: Creatinine, Calcium, Liver function tests (alanine aminotransferase [ALT], Aspartate Aminotransferase [AST], Alkaline Phosphatase, Bilirubin)
- Haematology (MHC, MCV, MCHC, Hemoglobin, Platelets, Leukocytes)

Urinalysis for safety:

- Urine pregnancy test as appropriate
- Microalbuminuria
- Creatinine

Other Variables which will be evaluated:

- Inflammatory markers, especially TNF-alfa, IL-1 beta, IL-2, IL-17
- Th2-deviation of cell-mediated immune response seen e.g. as increased ratio of IL-5,10, 13 in comparison with IFN-gamma, TNF-alfa, IL-1 beta and IL-17, and increase of T-regulatory cells
- C-peptide (90 minute value and AUC_{mean 0-120 min}) during an MMTT
- Proportion of patients with a stimulated maximum C-peptide level above 0.2 nmol/L
- Fasting C-peptide
- Hemoglobin A1c (HbA1c)
- Exogenous insulin dose per kg body weight and 24 hours
- Vitamin D levels in serum

Outcomes above are in agreement with the general Guidelines for Intervention Trials in subjects with newly diagnosed T1D defined by the Immunology of Diabetes Society (89).

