9.2 Adverse events, Serious Adverse Events and Pregnancy

9.2.1 Definitions of Adverse Events (AE)

An Adverse Event (AE) is defined as any untoward medical occurrence in a subject during a clinical study administered a medicinal product and which does not necessarily have a causal relationship with this treatment(s).

An AE can therefore be any unfavorable and unintended clinical sign or symptom, any illness or disease, which develops or worsens in intensity during the course of the trial. It also includes an

abnormal laboratory finding, if e.g., the abnormality results in trial withdrawal, is serious, is associated with clinical signs or symptoms, or is considered being of clinical relevance.

It could also include accidents and reasons for changes in medication (drug and/or dose), any medical/nursing/pharmacy consultation and admission to hospital/surgical operations.

Any new findings, clinically significant laboratory values or worsening of pre-existing condition must be reported as an AE by the investigator, whether or not considered related to the medicinal product(s).

Note that hospital admission and/or surgical operations for illness, which existed before the study drug was given or the subject was enrolled in the clinical trial and did not worsen during the study, are not AEs.

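### Etanercept is to stop for severe lymphopenia (5.4), but the haematology panel itemised in 9.1.1 has no differential or lymphocyte count to detect it

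*Combined protocol and SAP*

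**What the plan says.** Section 5.4 introduces the etanercept list with "Etanercept should not be continued if the patient after inclusion in the study develops/experiences". Among the entries are "Severe lymphopenia", anemia and thrombocytopenia. None of the three carries a numeric limit or a grade.

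Section 9.1.1 is the only place that itemises the blood count: "Haematology (MHC, MCV, MCHC, Hemoglobin, Platelets, Leukocytes". Section 6.2, item 7, sets the timing: "HbA1c, safety (haematology and chemistry), autoantibody titres (GAD65, IA-2), immunology are followed by blood samples at every visit". Section 6.3 and the legible haematology row of Table 2 name haematology without listing its components.

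Two other provisions bear on the point. Section 9.2.1 says "Any new findings, clinically significant laboratory values or worsening of pre-existing condition must be reported as an AE by the investigator". Section 6.7 describes a separate Safety Plan and says "This Safety Plan must be used in conjunction with this protocol". Section 9.1.1 also leads there, since it refers the reader to 6.3-6.7 for "laboratory measurements, physical examinations and neurological assessments (See section 6.3-6.7". That plan is not among the documents supplied.

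**The concern.** A stop that is defined by a blood count works only if the count is measured. For white cells the named panel gives only the total, and lymphocytes are one fraction of that total. A site that follows the protocol text exactly could hold a normal leukocyte result for a child whose lymphocyte count meets the stopping condition, and nothing in the scheduled safety bloods would show it.

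The patients are aged 8 to 17 and take a TNF blocker. Section 2.5 describes the risks of such therapy as mostly those of compromised immunity, and section 4.2.1 makes haematology a primary tolerability variable. A laboratory stop is worth most before an infection appears. What is at stake is patient safety during about three months of weekly dosing. Sample size and the descriptive tables are not affected.

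**Working it through.** **1. Match the blood-count stops in 5.4 to the panel in 9.1.1.**

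| Single-lineage stop (5.4) | Matching test (9.1.1) |
|---|---|
| Anemia | Hemoglobin |
| Thrombocytopenia | Platelets |
| Severe lymphopenia | None; total leukocytes only |

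The protocol keeps low total leukocytes and low lymphocytes apart: exclusion 24 in section 5.2 names leukopenia, whereas the stop in 5.4 names lymphopenia.

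**2. Look for a lymphocyte count elsewhere.** None appears in 6.2, 6.3, 6.7.1 or the legible rows of Table 2. Some row labels in the additional-sampling block of Table 2 did not survive text extraction, so the search is incomplete there. T-cell classification is listed in 6.3 under immunological tests and serves a secondary endpoint (4.2.2). No absolute count and no safety review of those results is stated.

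**3. Can a normal total hide the condition?** The documents give no limits, so these are assumptions: lower limit for leukocytes 4.0 x10^9/L; severe lymphopenia below 0.5 x10^9/L, range 0.2 to 1.0. The lymphocyte share below which a child meets the cut-off is cut-off / total leukocytes.

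- Total 4.0: 0.5/4.0 = 12.5% (0.2/4.0 = 5%; 1.0/4.0 = 25%).
- Total 7.0: 0.5/7.0 = 7.1% (0.2/7.0 = 2.9%; 1.0/7.0 = 14.3%).

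Neither child would be flagged for leukopenia. This shows that masking is possible. It does not show how often it happens.

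**4. When would a result help?** Weekly dosing from Day 1 within Days 1-90 (section 8.3) falls on Days 1, 8, ..., 85: (85 - 1)/7 + 1 = 13 doses. Visit windows are from 7.1, which dates Visit 4 from Visit 3 "so that the first and second GAD-Alum doses will be 30 days apart", within 3 days. Visit 4 can therefore fall from Day 27 + 27 = 54 to Day 33 + 33 = 66.

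| Visit | Doses left, nominal day | Doses left across the window |
|---|---|---|
| 3 | Day 30: 8 (Days 36-85); 8/13 = 62% | Days 27-28: 9; Days 29-33: 8 |
| 4 | Day 60: 4 (Days 64-85); 4/13 = 31% | Days 54-56: 5; Days 57-63: 4; Days 64-66: 3 |
| 5 | Day 90: 0 | Days 83-84: 1; Days 85-97: 0 |

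A seven-day delay in review from the nominal days costs one dose, leaving 7 at Visit 3 and 3 at Visit 4. Visits 3 and 4 are thus where a count can change treatment.

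**The case against.** The strongest reply is that the supplied text is not the whole safety arrangement. The heading of 6.7.1 sends the reader to the Safety Plan for etanercept precautions, and a differential could well be specified there; a site laboratory might also report one routinely. This stands. A reader might infer that lymphocytes go unmonitored in this trial, and the documents do not support that. They show only that the protocol's own panel does not require the count.

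A second reply is that the 5.4 list names conditions a patient may develop, not laboratory triggers. This also stands in part. A reader might infer that severe lymphopenia is the only etanercept stop without a scheduled test. It is not: no specific scheduled test during treatment is listed for cardiac disorder, SLE or malignancy, and tuberculosis is screened at Visit 1 only. The narrower comparison survives, because severe lymphopenia is defined by a blood count and its two neighbours are measured.

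Third, much of the risk is already handled. A low leukocyte total would be seen and could be acted on through adverse event reporting and investigator's discretion. Fever, infection with fever, marked tiredness or paleness interrupts etanercept under 6.7.1, and diaries are reviewed at every visit during treatment. These routes are real, but they need symptoms or a value that was measured. The DSMB's twice-yearly review is slow against a 90-day course.

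Finally, a reader might want to put a probability on seeing a case among about 20 patients. The documents do not allow it. Section 2.3 gives rates only for pancytopenia (under 1 in 1000) and aplastic anemia (under 1 in 10 000), which are different events. Any assumed rate of lymphopenia in general would overstate the narrower event that matters here.

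**Conclusion.** The mismatch between 5.4 and 9.1.1 is real and narrow. Of three single-lineage blood-count stops, one has no matching test in the named panel. The case left uncovered is asymptomatic severe lymphopenia with a normal leukocyte total. How often that occurs cannot be derived from the documents. What can be sized is the benefit of detection: 8 of 13 doses spared at nominal Visit 3, 4 of 13 at nominal Visit 4, and at most 1 at Visit 5.

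The conclusion assumes that the Safety Plan does not already require a differential and that no unreadable row of Table 2 supplies one. The masking shares rest on assumed limits; the dose counts rest on strict weekly dosing from Day 1. Even where a laboratory reports lymphocytes anyway, the supplied text gives no level at which the count is severe, so the stop would still be applied by individual judgement across about 10 sites. This is a cheap improvement worth considering, held with medium confidence.

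**What to change.** Add a white-cell differential with absolute lymphocyte count to the 9.1.1 haematology list, run on blood already drawn at Visit 2 (baseline), Visit 3 and Visit 4. Visit 5 is optional, since it spares 0-1 doses. Visit 1 is not needed for this purpose, because no entry criterion refers to lymphocytes. Require the Visit 3 and Visit 4 results to be reviewed before the next weekly etanercept dose, and state in 5.4 the count treated as severe. If the Safety Plan already contains this, cite it in 5.4 and 9.1.1 instead.

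Cost: 3 visits x 20 patients = about 60 extra results to review (80 with Visit 5) and a few lines of text, with no new visit or blood draw. The downside is some repeat tests, and possibly a skipped dose, for low counts that prove transient, for example during a minor viral infection.

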6.1 Study Design and Treatment

The trial is multicenter, open-label, pilot study in GADA positive T1D patients of either gender, 8.00 to 17.99 years old, diagnosed with T1D within 100 days at time of screening (Visit 1) and fasting C-peptide levels equal to or above 0.12 nmol/L. In total, approximately 20 patients will be recruited at approximately 10 sites in Sweden.

The patients will be assessed for eligibility at the screening visit (Visit 1) 10 to 21 days prior to the start of treatment. At each site, the screened patients will be assigned a sequential screening number (starting with 01) and this screening number together with the site number will be used as patient identification throughout the study (i.e. XX-XX).

Patients who qualify for inclusion in the study will then be enrolled in the study to receive investigational study drug at the subsequent visits according to table 1 below.

The patients will be followed for a total study period of 30 months which includes 9 visits to the site.

See table 1 below for an overview of the study visits.

Table 1. Study Visits

EDCR IIa	Screening	Intervention – Main Study Period					Follow-up Period	Study	
	Day -10 to -21 Screening	Day 1 Base- line	Day 30 Month 1	Day 60 Month 2	Day 90 Month 3	Day 180 Month 6	Day 270 Month 9	Day 450 Month 15	Day 900 Month 30
	Visit 1	Visit 2	Visit 3 ± 3	Visit 4 ± 3	Visit 5 ± 7	Visit 6 ± 7	Visit 7 ± 14	Visit 8 ± 14	Visit 9 ± 14
Appr 20 subjects		Vitamin I	Vitamin D 2 000 IU daily, from Day 1 to Day 450						
		Etanercept injections once weekly from Day 1 to 90							
			Prime injection GAD- Alum 20 μg	Boost injection GAD- Alum 20 μg					

6.2 Assessments and Procedures

- 1. Standard insulin treatment, education and psychosocial support for newly diagnosed T1D patients.
- 2. Normalization of fluid, electrolyte and acid-base balance.
- 3. Thereafter information about the study.
- 4. When the patients and parent(s) / legal guardian(s) have given their informed consent, at the latest 100 days after diagnosis, screening is performed with a fasting venous sample from patients who are eligible according to other criteria than C-peptide and GADA concentrations (Visit 1). Patients are also tested for tuberculosis, renal or liver disease at this visit (see section 5.3.1 and 5.3.2 above).
- 5. At Visit 2 (Baseline), Visit 6 (6 months), Visit 8 (15 months) and Visit 9 (30 months), assessment of residual endogenous insulin secretion by MMTT.
- 6. Blood sampling for Vitamin D in serum at Visit 1, and then after one month of treatment at Visit 3 (before the first GAD-alum treatment) and at Visit 8 (15 months)
- 7. HbA1c, safety (haematology and chemistry), autoantibody titres (GAD65, IA-2), immunology are followed by blood samples at every visit.
- 8. Exogenous insulin dose/24 hours, AEs and concomitant medication are registered at every visit.
- 9. Self-reported hypoglycaemia (defined as needing help from others and/or seizures and/or unconscious) registered at every Study Visit.
- 10. Any symptoms or signs of other medical problems should be treated at the discretion of the clinical doctor. Thus if a patient experiences symptoms and/or signs of infection that should be treated lege artis.

Examinations will be performed according to table 2 in Section 7 below, and in the order outlined in the case report form (CRF).

6.2.1 All Visits, Visit 1 through 9

Note that the patient should attend all study visits in the morning following an overnight fast (> 10 hours, water allowed).

For patients with evidence of an infection (including fever), the complete visit should be postponed for 5 days or until the patient has recovered.

6.2.2 Injections with GAD-Alum (Diamyd), Visits 3 and 4

Injections of GAD-alum (Diamyd) will be administered at Visits 3 and 4, subcutaneously in the stomach area.

After the injection, the patient shall remain in the vicinity of the study site for the next hour, and the injection site will be examined by investigator/study nurse 1 hour post injection.

6.2.3 Mixed Meal Tolerance Test (MMTT), Visits 2, 6, 8 and 9

The MMTT must be performed according to the instructions in the CRF.

The patient should:

- Come to the study site following an overnight fast (>10hr), i.e. the patient may not eat but is permitted to drink water
- Not take short acting/direct acting insulin within 6 hours before the MMTT. The patient is allowed to take base-insulin day/night before, but not in the morning before the MMTT.
- Patients with CSII (insulin pump) must continue with their basal dose insulin, but not add bolus dose during the last 6 hours before the MMTT
- Have a fasting plasma glucose level in the range defined by 4-12 mmol/L on the patient's home blood glucose meter in the morning of the test

If the patient does not fulfill all of the above criteria, the MMTT should be rescheduled and the patient should return to the study site within 5 days if possible.

If for safety reasons, subjects need to eat or take insulin, the visit should also be rescheduled.

6.3 Laboratory Tests and Examinations:

- 1. Immunological tests:
 - a. Autoantibodies (Anti-GAD65, Anti-Insulin, Anti-IA-2, ZnT8)
 - b. Relevant cytokines and chemokines are determined (see Table 2 and section 9.1.1 below)
 - c. T-cells are classified and studied (see Table 2 and section 9.1.1 below)
- 2. Genetics:
 - a. HLA determinations are done and genes related to diabetes development
 - b. Array studies to elucidate the importance of diabetes-related genes
- 3. Growth factors:
 - a. IGF-1 and related binding proteins and growth factors possibly related to beta cell growth and regeneration
- 4. Diabetes status:
 - a. HbA1c
 - b. Fasting glucose and fasting C-peptide
 - c. Meal stimulated glucose and C-peptide
- 5. Blood sampling for safety:
 - a. Hematology
 - b. Chemistry, including calcium
- 6. Urinalysis
 - a. Microalbuminuria
 - b. Creatinine
- 7. Other:

a. Vitamin D in serum

6.4 Medical History

A complete review of the subject's past medical history will be undertaken by and documented on the Medical History CRF.

All pre-existing conditions/diseases will be reported on the Medical History CRF page at the screening visit (Visit 1).

The subject's T1D diagnosis date and family history of T1D will also be documented.

6.5 Physical Examination and Neurological Examination

At the screening visit (Visit 1) the patient will undergo a general physical examination and a neurological examination and any findings will be reported as pre-existing conditions on the Medical History CRF page.

During the subsequent study visits the patient will be examined for any new medical conditions or worsening of the pre-existing ones. Any change in pre-existing conditions or new conditions must be entered on the AE page in the CRF and any medication given on the concomitant medication pages.

The patients will, in addition to the physical examinations by the physician, undergo a standardized clinical neurological examination at 0, 6, 9, 15 and 30 months. The neurological tests are performed in order to detect possible mild signs of neuromuscular disease such as disturbance of strength, balance, and coordination.

The neurological examination includes:

- Extremity reflexes
- Romberg (balance and coordination)
- Walk on a line, 2 meters (balance and coordination)
- Standing on 1 leg, left and right, 15 seconds per leg (balance and coordination)
- Finger-nose (coordination)
- Mimic (cranial nerves)
- Babinski reflex (central function)
- Muscle strength (shake hands) biceps, triceps, distal extensors, and flexors

These examinations may also be repeated between scheduled visits at the discretion of the investigator. Screening for neurological disease with electroencephalogram (EEG) is not included due to low sensitivity and specificity. However, if any signs of neurological dysfunction are detected, the patient should be referred to a neurologist for further evaluation.

